5.3 Subject Selection

The study sample will be drawn from patients who have received head and neck cancer therapy and have developed HNL secondary to their cancer treatment.

Patients will be recruited from the head and neck cancer clinic at Vanderbilt University and similar clinics at the other investigational sites(s). The patient must have undergone (or attempted and failed) complete decongestive therapy (CDT), or is unable to access CDT as outlined in the inclusion criteria. Only patients who meet the criteria listed below will be considered for the study. A total sample of 40 subjects (20 per group balanced within each site) will be enrolled and those withdrawn for lack of adherence will be replaced, thus we may enroll up to 50 individuals.

5.3.1 Inclusion Criteria :

- Age \geq 18 years
- A previous diagnosis of histologically defined head and neck cancer
- A diagnosis of head and neck lymphedema
- Must be able and willing to participate in all aspects of the study and provide informed consent prior to study participation
- Complete cancer treatment with no evidence of active cancer; all post-surgical swelling must be resolved.
- The head and neck garments must fit appropriately. For patients with a tracheostomy, the fit will be assessed to ensure that the garments do not interfere with their tracheostomy.
- The subject must have experienced at least one of the following:
 - Completion of phase 1 lymphedema care in the past 8 weeks
 - The inability to participate/complete phase 1 care due to:
 - lack of available therapist/clinic
 - lack of insurance coverage or funding to support cost of care.

5.3.2 Exclusion Criteria: Subjects will be determined to be ineligible for this study if they meet any of the criteria described below :

- Uncontrolled hyperthyroidism or parathyroidism (for which endocrinologist recommends against neck compression)
- Carotid sinus hypersensitivity syndrome
- Symptomatic carotid artery disease, as manifested by a recent transient ischemic attack (within 30 days), ischemic stroke, or amaurosis fugax (monocular visual ischemic symptoms or blindness)
- Symptomatic bradycardia in the absence of a pacemaker
- Internal jugular venous thrombosis, acute or within 3 months
- Increased intracranial pressure or other contraindications to internal or external jugular venous compression
- Acute radiation dermatitis, unhealed surgical scar, unhealed or open wound(s), surgical flap less than 6-8 week post-operative

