- Facial or head and neck dermal metastasis
- Acute facial infection (e.g., facial or parotid gland abscess)
- Any condition in which increased venous and lymphatic return is undesirable
- History of pulmonary edema or decompensated congestive heart failure with in six (6) week of enrollment.
- Subject is pregnant or trying to become pregnant

5.3.3 Subject Withdrawal or Early Termination:

Subjects will exit the study if they meet any of the following criteria:

- Subject death
- Subject voluntarily withdraws
- Subject experiences a serious adverse event that in the investigator's clinical judgment necessitates study discontinuation
- Subject acquires any of the exclusion criteria, except
 - In the case of a subject acquiring an infection, they may remain in the study per the discretion of the investigator. Detailed information regarding the infection, nature, treatment, and duration, will be recorded.
- Non-adherence with any study procedures as defined by no use of device during a consecutive 7-day period as documented on the diary or failure to complete required documents.

5.4 Dosage:

Wait-list Control Group: Subjects will continue their home care regimen as defined by their physician/healthcare provider. The home care regimen may include:

- self-MLD
- exercise
- skin care
- wearing an appropriate compression garment.

After 8 weeks, the subject will then receive treatment as outlined below in the investigational group if they so desire.

Investigational Group: Subjects in the investigational group will use the Flexitouch® pneumatic compression device in addition to the home care regimen defined by their treating physician/healthcare provider. The subject will complete two treatment sessions daily using the Flexitouch® head and neck system for the full 8 weeks of study participation. The twice daily treatment will include the H1 program for the head, neck and chest with an approximate 25-43 minute single cycle time as outlined in the Flexitouch® System User Guide (Appendix A). Instructions for the application of the head and neck garments are located in Chapter 6 of the Flexitouch® System User Guide (Appendix A). The home care regimen may include:

- self-MLD
- exercise
- skin care
- wearing an appropriate compression garment, if applicable

5.5 Study Timetable:

	1- 3months	4-6 months	7-9 months	10-14 months
IRB Review	X			
Enrollment	X	X	X	
Treatment		X	X	
Data Entry		X	X	
Data Analysis			X	
Manuscript Draft			X	
Publication				X

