7.2.2 Laboratory Testing

Women of childbearing potential, defined as premenopausal, intact ovaries and uterus, and not on birth control, will be tested for pregnancy using a self-administrator urine pregnancy test. If the pregnancy test is positive, the subject will be excluded from the study.

7.2.3 Feasibility (Appendix E):

7.2.3.1 Adherence and barriers (Both Groups): Subjects will keep a diary of device use and list barriers to use of device (investigational group). A self-care checklist will be completed each week they are in the study (both groups).

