12.3 Statistical Analysis Plan

Minimization of Bias: Stratified randomization to the study groups within each study site will be conducted. Given that this is a wait list/control design, blinding is not possible. Each subject will be assigned a study ID number that will be used for identification purposes in the data. The study statistician who will have no contact with any study participants and will conduct all analyses.

Missing Data: Randomly missing item responses within the study survey measures will be handled as specified by the measure developers. Nonrandom missing visit data are informative for this study (i.e., may speak to feasibility) – no imputation will be conducted.

Interim Analysis: Given that this is a feasibility study, no interim analyses will be conducted. The primary reason for early stoppage would be adverse events.

Aims:

Primary Aim: To determine the feasibility of use of the Flexitouch® Head and Neck Garment, specifically a) to evaluate implementation fidelity (adherence) and barriers to implementation fidelity, b) to establish safety, and c) to assess satisfaction.

Secondary Aim: To determine the preliminary efficacy of Flexitouch® Head and Neck Garment compared to a wait-list control for the following outcomes: a) reduction in swelling/inflammation, b) function (range of motion cervical, jaw, and shoulder), c) symptoms, and d) quality of life.

12.4 Statistical Analyses:

Aim 1 (feasibility): Descriptive statistics (percentages) will be used to summarize adherence to the protocol, barriers, adverse effects, and ratings of satisfaction. Comparison of the rates observed within each of the study groups will be compared using likelihood Chi-Square tests however it is expected that $\geq 75\%$ of the total number of participants enrolled in the study as a whole will complete the study. At the end of the study, it is expected that participants in the investigational group will report acceptable levels of satisfaction with the device, as indicated by 80% rating the satisfaction items above neutral.

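### Section 5.3.3 makes exit mandatory for incomplete documents, with no list and no tolerance, so subjects who still attend can be withdrawn, replaced and lost from the 75% completion figure

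*Combined protocol and SAP*

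**What the plan says.** Section 5.3.3 introduces its exit criteria as binding: "Subjects will exit the study if they meet any of the following criteria". The last criterion is non-adherence, defined as seven consecutive days without device use "as documented on the diary or failure to complete required documents". The section does not name the documents, say how many may be missed, or say what happens to a late form. Two other bullets in the list, on serious adverse events and on infection, leave room for the investigator's judgement. This one does not.

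Three other sections bear on the consequences.

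- **Section 5.3, replacement:** "those withdrawn for lack of adherence will be replaced, thus we may enroll up to 50 individuals". The synopsis caps replacements at 10.
- **Section 12.4, Aim 1:** at least 75% "of the total number of participants enrolled in the study as a whole will complete the study". Completion is not defined.
- **Section 12.3, missing data:** "Randomly missing item responses within the study survey measures will be handled as specified by the measure developers". Also, "Nonrandom missing visit data are informative for this study", and there is no imputation.

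The paperwork is set out in 7.2.3 and the 7.4 schedule. Both groups fill in a weekly self-care checklist and five questionnaires at weeks 4 and 8. The device group also keeps a diary and completes a post-treatment survey. Under 6.4 and 6.5, staff collect the checklists and go through the diary at visits, and subjects correct their own diary entries.

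**The concern.** Take the document limb as written. A subject attends weeks 1 and 4, uses the device and is willing to return, but has missed a form collected at week 4. Under 5.3.3 that subject exits, and under 5.3 is replaced. Unless completion is defined otherwise, the subject is also a non-completer under 12.4. The week-8 visit is lost although it could have been obtained. For endoscopy and cytokines this leaves no post-baseline value at all, because 7.4 schedules them only at baseline and week 8.

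The 75% figure is one of only two numeric feasibility expectations in the plan; the other is 80% rating satisfaction above neutral. If paperwork lapses become withdrawals, the trial could report poor retention among people who were in fact attending. Replacement cannot repair the figure, because its denominator is everyone enrolled. The limb can also be applied differently from site to site, so the same behaviour could be a completion at one site and a withdrawal at another.

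**Working it through.** **The plan's own figure.** Section 12.4 gives 80% power with 20 completers per group for 0.9 SD (NDI difference 9, SD 10, two-sided alpha 0.05). The normal approximation gives 20 per group and 81.2% power; the noncentral t with 38 df gives 79.2%. The figure reproduces, and it assumes 40 completers. The 75% expectation has no derivation. In counts it is 30 of 40, or 38 of 50 (0.75 × 50 = 37.5).

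**Document counts (device / wait-list), from 7.2.3 and 7.4.**

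- All post-baseline self-completed documents: wait-list 8 checklists + 5 questionnaires × 2 visits = 18; device 18 + 3 diary reviews + 1 post-treatment survey = 22.
- Leaving out documents due at week 8, when there is nothing left to exit from: device 22 − (5 questionnaires + 1 checklist + 1 diary review + 1 survey) = 14; wait-list 18 − (5 + 1) = 12.
- Also leaving out the week 5 to 7 checklists, which are collected at week 8: 14 − 3 = 11 and 12 − 3 = 9.

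**Formula.** Let p be the chance that any one document is completed. The plan gives no value, so p is an assumption. With independent misses, zero tolerance and no other dropout, a subject with k documents avoids exit with probability p^k. The number completing out of 40 is the sum of Binomial(20, p^k) for the device group and Binomial(20, p^m) for the wait-list group, where m is the wait-list count.

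| Documents counted | p | p^k / p^m | Mean completion | P(at least 30 of 40) |
|---|---|---|---|---|
| 22 / 18 | 0.99 | 80.2% / 83.5% | 81.8% | 90% |
| 22 / 18 | 0.98 | 64.1% / 69.5% | 66.8% | 18% |
| 22 / 18 | 0.95 | 32.4% / 39.7% | 36.0% | about 0% |
| 14 / 12 | 0.99 | 86.9% / 88.6% | 87.8% | 99% |
| 14 / 12 | 0.98 | 75.4% / 78.5% | 76.9% | 69% |
| 14 / 12 | 0.95 | 48.8% / 54.0% | 51.4% | 0.2% |
| 11 / 9 | 0.99 | 89.5% / 91.4% | 90.4% | 99.9% |
| 11 / 9 | 0.98 | 80.1% / 83.4% | 81.7% | 90% |
| 11 / 9 | 0.95 | 56.9% / 63.0% | 60.0% | 3% |

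**Break-even.** Solving (p^k + p^m)/2 = 0.75 gives p = 0.986 for 22/18, 0.978 for 14/12 and 0.972 for 11/9.

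**Replacement slots.** At p = 0.98, expected exits among the first 40 are 40 × (1 − 0.668) = 13.3, 40 × (1 − 0.769) = 9.2 and 40 × (1 − 0.817) = 7.3 on the three counts. The limb alone could take most or all of the 10 slots.

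**Clustered misses.** If misses cluster within subjects, the beta-binomial chance of no miss is the product over j = 0 to k − 1 of (a + j)/(a + b + j), with a = p(1/ρ − 1) and b = (1 − p)(1/ρ − 1). For 22/18 and ρ from 0.1 to 0.3, this gives 56–74% / 60–76% at p = 0.95 and 79–89% / 81–90% at p = 0.98. Clustering makes the problem milder.

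**The case against.** The strongest reply is that zero tolerance is a reading of 5.3.3, not its text. The word documents is plural and undefined, and the seven-day period may be meant to govern both limbs. That stands: one missed form is the literal reading, not the only one. But a mandatory exit rule that sites can read in two ways, and that feeds a primary-aim figure, still needs settling.

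Timing also limits the rule. Checklists are collected at weeks 1, 4 and 8, so a missed week-6 checklist comes to light at the final visit and cannot cause an early exit. Nor can the week-8 questionnaires or the post-treatment survey. This stands, and it is why the two smaller counts are shown. Diary review with corrections softens the rule further for the diary; no such correction is described for checklists or questionnaires.

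A reader might infer that 5.3.3 contradicts the missing-data plan. The documents do not support that. Section 12.3 covers items within a survey and missing visits, and contains no rule that a subject with a missed form is retained. It is a tension only.

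A reader might also infer that the rule removes device subjects disproportionately. The device group does have more documents, but at p = 0.98 the full count gives a gap of 20 × (0.695 − 0.641) = 1.1 subjects per 20. Of its four extra documents, two fall at week 8 and the other two are staff-reviewed diaries.

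**Conclusion.** The point holds as an unbounded, mandatory exit rule that, followed literally, withdraws and replaces randomised subjects who could still give week-8 data, and lowers a primary-aim figure. This is a stated rule with a poor result, not only a missing detail.

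Its size cannot be fixed from the documents. At an assumed 98% per document, the chance of reaching 30 of 40 is 18%, 69% or 90% depending on which documents count. At 99% it is at least 90% on every count, and at 95% it is under 5%. These figures rest on independent misses, equal p for all documents, no other dropout, and completion meaning never having met the document limb. Other dropout would lower them; clustered misses would raise expected completion.

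A reader might infer that the trial is likely to miss 75%. The documents do not support that: it depends on a rate they do not give. The 75% is also worded as an expectation, not a success criterion.

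**What to change.** Reconcile 5.3, 5.3.3, 12.3 and 12.4 as follows.

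- State that missing forms alone neither end study follow-up nor trigger replacement.
- Handle missing forms as missing data under 12.3, and report the percentage of required forms completed, by arm, as a feasibility result. List which forms are required.
- In 12.4, define a completer as a randomised subject who attends the week-8 visit, whatever single forms are missing.

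Whether device use continues in such a subject, and how the seven-day non-use limb works, are for the sponsor to settle and are not addressed here.

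The cost is a few sentences, with no new patients or data collection. There are two small downsides. The database will hold some subjects with incomplete forms. The wait-list arm will also have no adherence-based exit criterion, because device non-use cannot apply to it during the 8 weeks.

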6.1 Study Visit Summaries

6.2 Screening:

The subject will provide written informed consent prior to screening. The study will be explained to each subject. An Informed Consent Form (ICF) will be signed by each subject before study participation as mandated by FDA regulations and the institutional review board (IRB). (See Appendix B) A blank copy of the IRB approved informed consent form must be kept on-site and by Tactile Medical™. A copy of the ICF will be given to the subject to read and take home to consider, if they prefer. All the subject's questions must be answered prior to signing the ICF. Research procedures cannot be performed until the subject provides consent. The signed original for each subject must be kept in the subject's research records. A copy of the signed consent form will be given to each subject.

After informed consent is obtained, screening will commence. (See Appendix C: Screening Form) The subject's head and neck measurements will be taken to assist with garment size selection. For subjects with a tracheostomy, the fit will be accessed further to ensure that the garments do not interfere with their tracheostomy. The head and neck garment measuring guide is included in Appendix A. Should the head and neck measurements indicate the garment will not fit, no further information will be obtained and the subject will be withdrawn. After the garment fit has been confirmed the remaining inclusion and exclusion criteria will be evaluated to ensure that the subject meets all entrance criteria. The subject should not undergo any study specific procedures until after the informed consent process and screening processes are complete.

6.3 Baseline Visit:

The screening and baseline visit can occur on the same day or different days depending on the needs of the subject. At this visit, the subject will undergo the baseline data collection procedures as outlined in the Study Schedule of Activities in section 7.4.

Randomization:

After completing the informed consent process and baseline data collection (including the endoscopy) subjects enrolled at each site will be randomized (1:1) to either the investigational group or wait-list control group via the use of a computer-generated, permuted block program executed by the study biostatistician. Each site will have its own unique randomization list.

Subjects randomized to the investigational group at each site will follow the Study Schedule of Activities table in section 7.4 and will complete the study in 8 weeks. The subjects that are randomized to the waitlist group at each site will complete all study activities as outlined below in table 7.4. After completing the 8 weeks of the standard regimen, the subjects may choose to receive the same treatment as was implemented in the investigational group. No study data will be completed; however, patients opting to use the device will be seen at weeks 9, 12, and 16 for a documented safety check as outlined in section 7.4.

Research team members will provide the subjects with a self-care kit and provide instructions on how to use the kit. All subjects will leave the initial baseline visit with the self-care kit (Appendices D & E) that includes:

- Subject Diary (intervention group only)
- Self-care checklist
- Dates and Times for their upcoming appointments
- Contact information and instructions to call if any questions

6.4 Follow Up Visit(s):

The subject follow up visits will occur at 1 and 4 weeks (± 3 days). The study staff will collect the checklist and review the subject diary with the intervention patients during each visit to ensure that all entries are complete and understood by the study staff. Any corrections must be made by the subject, and initialed and dated by them. At the visit, the subject will undergo the study procedures as outlined in the Study Schedule of Activities in section 7.4.

6.5 Final Visit:

The final study visit will occur at 8 weeks (± 3 days). At this visit, the subject will undergo the study procedures as outlined in the Study Schedule of Activities in section 7.4. The study staff will collect the checklist and review the subject diary with the subject during each visit to ensure that all entries are complete and understood by the study staff. Any corrections must be made by the subject, and initialed and dated by them.

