5.1 Study Design

This study is an open label, multi-site, stratified by site, randomized, wait list control, pilot study. Vanderbilt University will serve as the multi-site coordinating center.

Within each study site:

5.2 Study Endpoints :

5.2.1 Primary Endpoints: The primary endpoint will occur when subjects complete the 8th week of treatment and provide: a) evaluation of implementation fidelity (adherence) and barriers to implementation fidelity, b) review of adverse events, and c) report satisfaction.

5.2.2 Secondary Endpoints: The secondary endpoints will be a) reduction in swelling/inflammation, b) function (range of motion cervical, jaw, and shoulder), c) symptoms, and d) quality of life.

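### Reviewing the diary for completeness at weeks 1, 4 and 8 invites recalled entries into adherence, the first primary component, and the analysis would not set them apart

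*Combined protocol and SAP*

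**What the plan says.** Section 5.2.1 lists what subjects provide at week 8, beginning with "a) evaluation of implementation fidelity (adherence) and barriers to implementation fidelity, b) review of adverse events"; satisfaction comes third. Section 7.2.3.1 names the record of device use: "Subjects will keep a diary of device use and list barriers to use of device (investigational group"). It adds a second self-report record for both arms: "A self-care checklist will be completed each week they are in the study (both groups"). The schedule in 7.4 gives the diary as the source for adherence and for barriers, in the intervention group only, at weeks 1, 4 and 8.

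On visit timing, 6.4 says "The subject follow up visits will occur at 1 and 4 weeks" and 6.5 says "The final study visit will occur at 8 weeks", each with a window of 3 days either way. At the follow-up visits staff are to "review the subject diary with the intervention patients during each visit to ensure that all entries are complete and understood by the study staff", and 6.5 has the same instruction for the final visit. On changes, both sections say "Any corrections must be made by the subject, and initialed and dated by them".

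The diary also feeds an exit criterion in 5.3.3: "no use of device during a consecutive 7-day period as documented on the diary or failure to complete required documents".

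Section 12.4 summarizes adherence in percentages. It gives no denominator, no rule for a session left blank, and no rule for an entry made or changed at a visit. The device log described in 8.0 covers location, assignment, return, disinfection and disposition; usage is not among the items listed.

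**The concern.** Asking staff to see that entries are understood is ordinary source review. Asking them to see that entries are complete is different when the record is a daily diary of the outcome itself. If a session is blank, the easiest way to meet the instruction is for the subject to write something at the visit, days or weeks after the session. Nothing in the supplied text lets a blank stay blank or limits how late an entry may be made.

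The likely direction is upward. The subject is answering in front of study staff, and under 5.3.3 both a week without documented use and incomplete documents are grounds for exit. Once blanks are filled, the reported percentage also loses the information on how many sessions had no entry before the visit. That matters because adherence is a main product of this pilot and would inform whether a twice-daily regimen is carried into a later trial.

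**Working it through.** The plan states no adherence figure, so there is none to reproduce. The benchmarks in 12.4 are for completion (at least 75%) and satisfaction (80%).

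**Planned sessions.** Section 5.4 gives two sessions a day for 8 weeks: 2 × 7 × 8 = 112 per subject.

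**Gaps between diary reviews** (visits at days 7, 28 and 56, each ±3 days):

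| Interval | Nominal days | Longest with windows | Planned sessions (nominal) |
|---|---|---|---|
| Baseline to week 1 | 7 | 7 + 3 = 10 | 14 |
| Week 1 to week 4 | 28 − 7 = 21 | 31 − 4 = 27 | 42 |
| Week 4 to week 8 | 56 − 28 = 28 | 59 − 25 = 34 | 56 |

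The two long intervals hold 42 + 56 = 98 of 112 sessions, or 87.5%. The first interval is short and adds little to the problem.

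**How far recalled entries could move the figure.** Let *a* be true adherence and *b* the share of undone sessions recorded as done. Recorded adherence is *a* + *b*(1 − *a*). Both inputs are assumptions; the documents give neither.

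| Assumed true adherence | b = 10% | b = 25% | b = 50% |
|---|---|---|---|
| 60% | 64% | 70% | 80% |
| 80% | 82% | 85% | 90% |

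**Why blanks should not simply be counted as not done.** Let *q* be the share of sessions left blank, *r* the share done among recorded entries, and *u* the true share done among blanks. True adherence is (1 − *q*)*r* + *qu*. Assume *q* = 20%, *r* = 70% and *u* = 50%:

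- truth: 0.8 × 0.7 + 0.2 × 0.5 = 66%
- blanks as not done: 0.8 × 0.7 = 56%, too low
- recorded entries only: 70%, slightly too high
- all blanks filled as done: 0.56 + 0.20 = 76%, too high

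The lowest and highest figures always differ by *q*, here 20 percentage points. That width can be reported only if blanks are left visible.

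**Denominator.** With the final visit at day 53 to 59, planned sessions run from 106 to 118. Early exits have fewer, so a fixed 112 does not fit every subject.

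**The case against.** The strongest reply is that 6.4 and 6.5 describe normal source-document review with an audit trail. Staff do not write in the diary; the subject does, with initials and a date. An entry of not used makes the diary just as complete as an entry of used. The exit rule gives little reason to inflate broadly: one recorded session in any 7 days avoids the non-use limb, and a subject at 60% does about 8 of 14 sessions a week (0.6 × 14 = 8.4). The diary form, the checklist and the device user guide are in appendices that are not in the supplied text, so they may contain dated fields or rules on late entries.

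Most of this stands, and it limits what can be said. A reader might infer that the plan has missed sessions filled from memory and that adherence is therefore overstated. The text does not order that, and overstatement is an inference. A reader might also see a contradiction with 12.3, which calls nonrandom missing data informative, but that sentence is about missing visit data and reaches diary blanks only by analogy. Nor can the diary be called the only source of device-use data while the checklist's content is unknown.

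The reply does not answer two things. The instruction presses for complete entries with no allowance for a blank. And although dated corrections could be identified, 12.4 does nothing with them.

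**Conclusion.** The point holds as a moderate one. A primary component rests on self-report, a stated visit procedure invites recalled entries over gaps of 21 and 28 days covering 87.5% of planned sessions, and the analysis would count those entries the same as earlier ones. The bias is probably upward. Its size cannot be computed from the documents; the 64% to 80% illustration rests wholly on assumed values.

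It would go too far to say that the regimen would be declared feasible when it is not. The plan sets no adherence threshold, so no formal decision turns on this figure. The sample-size calculation is unaffected.

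The conclusion assumes that the unseen appendices do not already restrict or mark late entries, and that some sessions will be blank when the diary is reviewed. Even so, this is more than a request for detail, because the instruction in 6.4 and 6.5 itself creates the problem.

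**What to change.** - **Sections 6.4 and 6.5.** Have staff clarify illegible or ambiguous entries only, not prompt subjects to fill unrecorded sessions, and flag any entry made or changed at a visit. The existing initials and date supply most of what the flag needs.
- **Collection.** Collect the diary weekly in REDCap with the self-care checklist, which is already weekly. This shortens the longest nominal interval between collections from 28 days to 7. It does not prove that an entry was made on the day.
- **Section 12.4.** Report adherence per subject over the sessions planned for that subject's actual time in the study, excluding visit-made entries. Show the range beside it: unrecorded sessions as not done, recorded entries only, and late entries included. No single one of these should be read as the truth. The recorded-entries figure needs a diary form on which a session can be entered as not done.
- **Section 8.0.** If the controller stores usage, which the documents do not state, read it when the controller is returned and report it beside the diary.

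The cost is protocol wording, one weekly form and a few lines in the analysis section. The downside is slightly more missing diary data and a reported adherence figure that is somewhat lower or has a wider range.
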